1.2 Secondary Objectives

- 1.2.1 To assess the safety/tolerability and further characterize the safety profile of selinexor in PMF, PET-MF, or PPV-MF patients refractory or intolerant to ruxolitinib and/or any other experimental JAK1/2 inhibitors.

Secondary Endpoints: rate of adverse events (AEs) and serious adverse events (SAEs).

- 1.2.2 To further assess the efficacy and clinical activity of selinexor (by means of reduction in symptoms, overall response, and overall survival) in subjects with myelofibrosis (PMF, PET-MF, or PPV-MF) refractory or intolerant to ruxolitinib and/or any other experimental JAK1/2 inhibitors.

Secondary Endpoints:

- Percent change of spleen volume as measured by MRI or CT abdomen.
- Proportion of patients with $\geq 50\%$ reduction of total symptoms score as measured by the MPN-Symptoms Assessment Form (MPN-SAF) from baseline to after 6 cycles of treatment. Patients who do not complete six cycles of therapy will be considered non responders, but their data will still be reported. Patients who do not complete six cycles of treatment will receive the MPN-SAF assessment at cycle 7 day 1, or at discontinuation of therapy (see section 11.4.2).
- Overall response rate according to the 2013 IWG-MRT consensus criteria for treatment response in primary and secondary MF (post-PV and post-ET).
- Overall survival at 24 months from the initiation of study therapy

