2 BACKGROUND

2.1 Myelofibrosis

The classic *BCR-ABL* negative myeloproliferative neoplasms (MPNs) encompass polycythemia vera (PV), essential thrombocythemia (ET) and primary myelofibrosis (MF). MF is characterized by clonal hematopoietic stem cell proliferation and bone marrow reticulin fibrosis, leading to ineffective erythropoiesis, elevated inflammatory cytokines, and marked extramedullary hematopoiesis.¹ The prevalence of MF in the United States is estimated to be 4-6 cases per 100,000 people with a median age of 60 to 65 years at diagnosis.² MF can present *de novo* (primary MF) or as secondary from PV (post-PV MF or PPV-MF) or ET (post-ET MF or PET-MF). Cytopenias, thromboembolism, symptomatic splenomegaly, and leukemic transformation account for the major morbidity of MF patients. The survival of MF patients is significantly reduced compared to age-matched controls as well as PV and ET patients. In addition, many MF patients have low quality of life (QoL) and experience debilitating constitutional symptoms including fatigue, anorexia, night sweats and weight loss.^{3,4} Various tools have been developed and validated in large cohorts of MPN patients for

the assessment of disease-related symptoms. The MPN symptom assessment form (MPN-SAF) is a 27-item tool that allows for objective assessment of MPN symptoms and is validated in large cohort of MPN patients (including MF). A short abbreviated tool, the MPN-SAF Total Symptom Score (MPN-SAF TSS), includes the 10 most common symptoms in patients with MPN and is also a validated tool to assess symptom burden in MF patients.^{5,6} A $\geq 50\%$ reduction in the total symptoms score is considered to be a valid end point in clinical trials of MF patients.⁷⁻¹⁰

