10.2.2 Efficacy Based on Patient Reported Outcomes

Subjects will complete the Myeloproliferative Neoplasm Symptom Assessment Form (MPN-SAF, see Appendix 7) at baseline and at each subsequent clinic visit (C1D8, C1D15, D1 of each subsequent cycle, EOT). Their Total Symptoms Score (TSS) will be calculated at each time point.

A symptoms response is defined per IWG-MRT criteria²⁶ as a $\geq 50\%$ reduction in the MPN-SAF TSS. See Appendix 5 for details.

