6. Transfusion dependency before study enrollment is defined as transfusions of at least 6 units of PRBCs, in the 12 weeks prior to study enrollment, for a hemoglobin level of < 85 g/L, in the absence of bleeding or treatment-induced anemia. In addition, the most recent transfusion episode must have occurred in the 28 days prior to study enrollment. Response in transfusion-dependent patients requires absence of any PRBC transfusions during any consecutive "rolling" 12-week interval during the treatment phase, capped by a hemoglobin level of ≥ 85 g/L.
7. In splenectomized patients, palpable hepatomegaly is substituted with the same measurement strategy.
8. Spleen or liver responses must be confirmed by imaging studies where a $\geq 35\%$ reduction in spleen volume, as assessed by MRI or CT, is required. Furthermore, a $\geq 35\%$ volume reduction in the spleen or liver, by MRI or CT, constitutes a response regardless of what is reported with physical examination.
9. Symptoms are evaluated by the MPN-SAF TSS. The MPN-SAF TSS is assessed by the patients themselves and this includes fatigue, concentration, early satiety, inactivity, night sweats, itching, bone pain, abdominal discomfort, weight loss, and fevers. Scoring is from 0 (absent/as good as it can be) to 10 (worst imaginable/as bad as it can be) for each item. The MPN-SAF TSS is the summation of all the individual scores (0-100 scale). Symptoms response requires $\geq 50\%$ reduction in the MPN-SAF TSS.
10. Progressive disease assignment for splenomegaly requires confirmation by MRI or CT showing a $\geq 25\%$ increase in spleen volume from baseline. Baseline values for both physical examination and imaging studies refer to pretreatment baseline and not to post-treatment measurement.
 - a. Thiele J, Kvasnicka HM, Facchetti F, van der Walt J, Orazi A. European consensus on grading bone marrow fibrosis and assessment of cellularity. *Haematologica*. 2005;90(8):1128-32.

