16.6 Appendix 6 - Screening Symptoms Form

Patient Initials: _____

Patient Study ID: _____

Please fill out all questions reflecting how these symptoms affected you at their worst moment over the past 7 days. Please give the answer that best reflects your opinion.

Symptom	1 to 10 (0 if absent) ranking 1 is most favorable and 10 least favorable
1. During the past 7 days, how severe were your worst night sweats (or feeling hot or flushed) due to MF?	(Absent) 0 1 2 3 4 5 6 7 8 9 10 (Worst Imaginable)
2. During the past 7 days, how severe was your worst itchiness due to MF?	(Absent) 0 1 2 3 4 5 6 7 8 9 10 (Worst Imaginable)
3. During the past 7 days, how severe was your worst abdominal discomfort (feel uncomfortable, pressure or bloating) due to MF?	(Absent) 0 1 2 3 4 5 6 7 8 9 10 (Worst Imaginable)
4. During the past 7 days, how severe was your worst pain under the ribs on the left side due to MF?	(Absent) 0 1 2 3 4 5 6 7 8 9 10 (Worst Imaginable)
5. During the past 7 days, how severe was your worst fullness (early satiety) you had after beginning to eat, due to MF?	(Absent) 0 1 2 3 4 5 6 7 8 9 10 (Worst Imaginable)
6. During the past 7 days, how severe was your worst bone or muscle pain due to MF (not joint or arthritis pain)?	(Absent) 0 1 2 3 4 5 6 7 8 9 10 (Worst Imaginable)
7. During the past 7 days, what was the worst degree of inactivity (work or social activities) you had due to MF (not joint or arthritis pain)?	(Absent) 0 1 2 3 4 5 6 7 8 9 10 (Worst Imaginable)

For Investigators/site staff:

Please confirm the criterion based on assessment of subject's active symptoms of myelofibrosis.

Criterion Review	Confirmation
A symptoms score of at least 5 on at least 1 of the symptoms	 Yes  No
A symptoms score of 3 or greater on at least 2 of the symptoms	 Yes  No

Investigator signature: _____

Date: _____

16.7 Appendix 7 - Myeloproliferative Neoplasms Symptom Assessment Form- Total Symptom Score (MPN-SAF TSS) Form

Patient Initials: _____

Patient Study ID: _____

Study Time Point (cycle/day): _____

Date: _____

Please fill out all questions by circling the one number that best describes your symptoms at their worst moment. Please give the answer that best reflects your opinion.

Symptom	1 to 10 (0 if absent) ranking 1 is most favorable and 10 least favorable

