Please rate your fatigue (weariness, tiredness) by circling the one number that best describes your WORST level of fatigue during past 24 hours	(No Fatigue) 0 1 2 3 4 5 6 7 8 9 10 (Worst Imaginable)

Circle the one number that describes how, during the PAST WEEK how much difficulty you have had with each of the following symptoms	
Filling up quickly when you eat (Early satiety)	(Absent) 0 1 2 3 4 5 6 7 8 9 10 (Worst Imaginable)
Abdominal discomfort	(Absent) 0 1 2 3 4 5 6 7 8 9 10 (Worst Imaginable)
Inactivity	(Absent) 0 1 2 3 4 5 6 7 8 9 10 (Worst Imaginable)
Problems with concentration (compared to prior to my MPD)	(Absent) 0 1 2 3 4 5 6 7 8 9 10 (Worst Imaginable)
Numbness/ Tingling (in my hands and feet)	(Absent) 0 1 2 3 4 5 6 7 8 9 10 (Worst Imaginable)
Night sweats	(Absent) 0 1 2 3 4 5 6 7 8 9 10 (Worst Imaginable)
Itching (pruritus)	(Absent) 0 1 2 3 4 5 6 7 8 9 10 (Worst Imaginable)
Bone pain (diffuse, not joint pain or arthritis)	(Absent) 0 1 2 3 4 5 6 7 8 9 10 (Worst Imaginable)
Fever (>100 F)	(Absent) 0 1 2 3 4 5 6 7 8 9 10 (Daily)
Unintentional weight loss (last 6 months)	(Absent) 0 1 2 3 4 5 6 7 8 9 10 (Worst Imaginable)

What is your Overall Quality of Life?	(As good as it can be) 0 1 2 3 4 5 6 7 8 9 10 (As bad as it can be)
---------------------------------------	---

Patient signature: _____

Date: _____

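### Does the MPN-SAF TSS form, with more rows than the score has items and no rule for a zero baseline, leave the symptom response undefined?

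*Combined protocol and SAP*

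**What the plan says.** Section 1.2.2 sets a 50% threshold for a secondary endpoint, which it words as a "reduction of total symptoms score as measured by the MPN-Symptoms Assessment Form (MPN-SAF) from baseline to after 6 cycles of treatment". Anyone stopping before the sixth cycle is finished counts as a non-responder.

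Section 10.2.2 names the instrument and the schedule: "Subjects will complete the Myeloproliferative Neoplasm Symptom Assessment Form (MPN-SAF, see Appendix 7) at baseline and at each subsequent clinic visit". It then says "Their Total Symptoms Score (TSS) will be calculated at each time point", defines response as a fall of at least 50%, and refers to Appendix 5 for details.

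Appendix 5, note 9, names the scored items: fatigue, concentration, early satiety, inactivity, night sweats, itching, bone pain, abdominal discomfort, weight loss and fevers. Each runs from 0 to 10, and "The MPN-SAF TSS is the summation of all the individual scores (0-100 scale". Section 2.1 agrees on the count: the TSS "includes the 10 most common symptoms in patients with MPN".

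The Appendix 7 form, headed "Total Symptom Score (MPN-SAF TSS) Form", has eleven symptom rows. The one not in note 9 is "Numbness/ Tingling (in my hands and feet". Below the symptom rows, and apart from them, is one further question: "What is your Overall Quality of Life". Every row is scored 0 to 10.

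Section 11.4.2 defines the efficacy population as all enrolled patients who received at least one dose. Section 11.5.2 reports the symptom-response proportion with an exact 95% interval and is silent on a baseline TSS of 0.

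**The concern.** A form headed as the TSS form invites the reader to add up everything on it, and that total is not the TSS. An extra row that stays put while the others improve dilutes the percentage fall. An extra row that improves sharply inflates it. A patient near the 50% line could therefore be classified wrongly in either direction.

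The second worry is the denominator. Under section 5.1.5, a patient can enter on a spleen of at least 10 cm alone, or on intolerance with a spleen of at least 5 cm, with no symptom score required. If such a patient records 0 on every item at baseline, percentage change is a division by zero.

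Symptom response is a named secondary endpoint and one route to clinical improvement, which counts in the overall response rate. With 24 patients, each reclassification moves a proportion by 1/24 = 4.2 percentage points.

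**Working it through.** **1. Reproduce the stated range.** Maximum score = number of items × 10.

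- Ten items of note 9: 10 × 10 = 100, as stated.
- Eleven symptom rows of Appendix 7: 11 × 10 = 110.
- Those rows plus quality of life: 12 × 10 = 120.

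Only the ten-item sum fits the stated scale.

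**2. Match the list to the form.** Each of the ten items in note 9 has exactly one row in Appendix 7. Two rows are left over: numbness/tingling and overall quality of life. The scored set therefore follows from note 9 by elimination, and section 10.2.2 sends the analyst there.

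**3. Size of the error if note 9 were ignored.** Percentage fall = (baseline − follow-up) / baseline. The patient scores below are assumed; the documents give none.

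| Ten items | Numbness | Ten-item fall | Eleven-row fall |
|---|---|---|---|
| 40 to 20 | 8 to 8 | 20/40 = 50.0%, response | (48 − 28)/48 = 41.7%, no response |
| 40 to 21 | 8 to 2 | 19/40 = 47.5%, no response | (48 − 23)/48 = 52.1%, response |

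In general, take a ten-item baseline T and a stable numbness score b. The eleven-row total halves only if the ten-item fall is at least 50% × (1 + b/T):

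- T = 40, b = 2: 52.5%
- T = 40, b = 8: 60%
- T = 20, b = 8: 70%

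These are the effects of a scoring mistake. Under the score as defined, b does not enter and the threshold is 50%.

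**4. Baseline TSS of 0.** Response requires a reduction. From 0, the lowest possible score, no reduction can occur, so the patient is not a responder. Section 11.4.2 keeps every treated patient in the efficacy population, so the patient also stays in the denominator. This matches section 1.2.2, which counts non-completers as non-responders.

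The alternative is to drop such patients. Let k be their number (not given in the documents) and assume 8 responders and 24 treated. The intervals are exact (Clopper-Pearson) 95%.

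| k dropped | Rate | 95% interval |
|---|---|---|
| 0 | 8/24 = 33.3% | 15.6 to 55.3 |
| 1 | 8/23 = 34.8% | 16.4 to 57.3 |
| 2 | 8/22 = 36.4% | 17.2 to 59.3 |
| 6 | 8/18 = 44.4% | 21.5 to 69.2 |

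The last row assumes that a quarter of the trial starts with no symptoms at all. A TSS of 0 needs a zero on all ten items, including fatigue, early satiety and abdominal discomfort. Every entry route in section 5.1.5 requires a spleen palpable at least 5 cm below the costal margin, so large k is unlikely, although the documents cannot exclude it.

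**The case for a change.** The best case for a change is that elimination takes more effort than it should. Note 9 introduces its list with open wording and then sums all individual scores. Its item anchors include the good-to-bad phrasing that, on the form, belongs only to the quality-of-life row. Numbness/tingling sits unmarked in the middle of the symptom block. Sections 1.2.2 and 10.2.2 use the name MPN-SAF, which section 2.1 gives to a separate 27-item tool. On the zero baseline, the non-responder rule in section 1.2.2 covers only non-completers, and a careless inequality (follow-up no more than half of baseline) would count 0 to 0 as a response. The study is open label and 12 patients had been dosed by protocol version 7, so a rule first written after the scores are seen could look chosen to suit.

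It stands that the form lacks a label and that the zero-baseline rule is unwritten. It does not follow that the score or the rate is undetermined. The 0-to-100 range closes the list whatever the introductory wording, section 10.2.2 points to the form and to Appendix 5, and the plain meaning of a reduction excludes 0 to 0. An analyst following the text has one score and one denominator to use, so little room is left for a choice driven by the data.

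A rate among patients with baseline TSS above 0, or a mean change in TSS, could reasonably be reported as well. Neither corrects a wrong figure. The mean change would also need its own decision on values taken at early discontinuation.

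**Conclusion.** No change follows. The mismatch between form and score is a labelling gap, and the zero baseline is an edge case that analysts would settle sensibly from the existing text. Followed as written, the plan gives a ten-item TSS on 0 to 100 and an all-treated response rate in which a patient starting at 0 is a non-responder.

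The shifts across the 50% line require a departure from note 9 and rest on assumed scores. The denominator effect is nil at k = 0 and 1.5 percentage points at k = 1 (34.8% − 33.3%), assuming 8 responders among 24. It becomes large only at values of k that nothing in the documents supports.

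The endpoint is descriptive, with no hypothesis test. Where symptom response feeds clinical improvement, Appendix 5 also requires benefit lasting at least 12 weeks without progression or worsening cytopenia, which limits the effect of a marginal misclassification. The spleen-volume primary endpoint and the sample size do not depend on the TSS.

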16.6 Appendix 6 - Screening Symptoms Form

Patient Initials: _____

Patient Study ID: _____

Please fill out all questions reflecting how these symptoms affected you at their worst moment over the past 7 days. Please give the answer that best reflects your opinion.

Symptom	1 to 10 (0 if absent) ranking 1 is most favorable and 10 least favorable
1. During the past 7 days, how severe were your worst night sweats (or feeling hot or flushed) due to MF?	(Absent) 0 1 2 3 4 5 6 7 8 9 10 (Worst Imaginable)
2. During the past 7 days, how severe was your worst itchiness due to MF?	(Absent) 0 1 2 3 4 5 6 7 8 9 10 (Worst Imaginable)
3. During the past 7 days, how severe was your worst abdominal discomfort (feel uncomfortable, pressure or bloating) due to MF?	(Absent) 0 1 2 3 4 5 6 7 8 9 10 (Worst Imaginable)
4. During the past 7 days, how severe was your worst pain under the ribs on the left side due to MF?	(Absent) 0 1 2 3 4 5 6 7 8 9 10 (Worst Imaginable)
5. During the past 7 days, how severe was your worst fullness (early satiety) you had after beginning to eat, due to MF?	(Absent) 0 1 2 3 4 5 6 7 8 9 10 (Worst Imaginable)
6. During the past 7 days, how severe was your worst bone or muscle pain due to MF (not joint or arthritis pain)?	(Absent) 0 1 2 3 4 5 6 7 8 9 10 (Worst Imaginable)
7. During the past 7 days, what was the worst degree of inactivity (work or social activities) you had due to MF (not joint or arthritis pain)?	(Absent) 0 1 2 3 4 5 6 7 8 9 10 (Worst Imaginable)

For Investigators/site staff:

Please confirm the criterion based on assessment of subject's active symptoms of myelofibrosis.

Criterion Review	Confirmation
A symptoms score of at least 5 on at least 1 of the symptoms	 Yes  No
A symptoms score of 3 or greater on at least 2 of the symptoms	 Yes  No

Investigator signature: _____

Date: _____

16.7 Appendix 7 - Myeloproliferative Neoplasms Symptom Assessment Form- Total Symptom Score (MPN-SAF TSS) Form

Patient Initials: _____

Patient Study ID: _____

Study Time Point (cycle/day): _____

Date: _____

Please fill out all questions by circling the one number that best describes your symptoms at their worst moment. Please give the answer that best reflects your opinion.

Symptom	1 to 10 (0 if absent) ranking 1 is most favorable and 10 least favorable
Please rate your fatigue (weariness, tiredness) by circling the one number that best describes your WORST level of fatigue during past 24 hours	(No Fatigue) 0 1 2 3 4 5 6 7 8 9 10 (Worst Imaginable)

Circle the one number that describes how, during the PAST WEEK how much difficulty you have had with each of the following symptoms	
Filling up quickly when you eat (Early satiety)	(Absent) 0 1 2 3 4 5 6 7 8 9 10 (Worst Imaginable)
Abdominal discomfort	(Absent) 0 1 2 3 4 5 6 7 8 9 10 (Worst Imaginable)
Inactivity	(Absent) 0 1 2 3 4 5 6 7 8 9 10 (Worst Imaginable)
Problems with concentration (compared to prior to my MPD)	(Absent) 0 1 2 3 4 5 6 7 8 9 10 (Worst Imaginable)
Numbness/ Tingling (in my hands and feet)	(Absent) 0 1 2 3 4 5 6 7 8 9 10 (Worst Imaginable)
Night sweats	(Absent) 0 1 2 3 4 5 6 7 8 9 10 (Worst Imaginable)
Itching (pruritus)	(Absent) 0 1 2 3 4 5 6 7 8 9 10 (Worst Imaginable)
Bone pain (diffuse, not joint pain or arthritis)	(Absent) 0 1 2 3 4 5 6 7 8 9 10 (Worst Imaginable)
Fever (>100 F)	(Absent) 0 1 2 3 4 5 6 7 8 9 10 (Daily)
Unintentional weight loss (last 6 months)	(Absent) 0 1 2 3 4 5 6 7 8 9 10 (Worst Imaginable)

What is your Overall Quality of Life?	(As good as it can be) 0 1 2 3 4 5 6 7 8 9 10 (As bad as it can be)
---------------------------------------	---

Patient signature: _____

Date: _____

16.8 Appendix 8 – Primary Myelofibrosis Dynamic International Prognostic Scoring System (DIPSS)

The DIPSS score assigns points for the following five variables:

Prognostic Variable	Point per Factor
Age > 65 years	1
Hemoglobin < 10 g/dL	2
White Blood Cells > 25 K/uL	1
Circulating Blasts \geq 1%	1
Constitutional Symptoms*	1

Total risk score	Risk category	Median overall survival
0	Low	not reached
1 to 2	Intermediate-1	14.2 years
3 to 4	Intermediate-2	4 years
5 to 6	High	1.5 years

- *Constitutional symptoms include:
 - Weight loss >10% of the baseline value in the year preceding PMF diagnosis
 - Unexplained fever or excessive sweats persisting for more than one month.

